4.3.2 Main analytical approach

All data collected will be presented in the form of individual patient listings. Relevant plots of efficacy endpoints by patient age over time will be provided.

4.3.3 Sensitivity analysis

Not applicable.

4.3.4 Supplementary analyses

Not applicable.

4.3.5 Subgroup analyses

Due to the small number of patient population, subgroup analyses will not be performed.

4.4 SECONDARY ENDPOINT(S) ANALYSIS

See Section 4.7 Safety Analysis.

4.4.1 Key/Confirmatory secondary endpoint(s)

Not applicable.

4.4.1.1 *Definition of endpoint(s)*

Not applicable.

4.4.1.2 *Main analytical approach*

Not applicable.

4.4.2 *Supportive secondary endpoint(s)*

Not applicable.

4.5 TERTIARY/EXPLORATORY ENDPOINT(S) ANALYSIS

4.5.1 *Definition of endpoint(s)*

Urinary oligosaccharide (Hex4) levels will be measured by a central laboratory every 6 months to study month 24 and then every 12 months after that.

4.5.2 *Main analytical approach*

Nominal and change from baseline will be summarized by visit.

4.6 MULTIPLICITY ISSUES

There is no issue with multiplicity.

4.7 SAFETY ANALYSES

All safety analyses will be performed on the FAS population as defined in [Section 3](#); unless otherwise specified, safety analyses will be descriptive, and no testing is planned.

4.7.1 *Extent of exposure*

Duration on study drug and number of study drug infusions will be presented using summary statistics. Frequency and percentages of patients who receive therapy up to certain time intervals and until the end of study will also be presented.

The extent of IMP exposure and compliance will be assessed by the duration of IMP exposure, total dose received at each study visit, cumulative dose received during the study period, and percentages of planned infusions received.

Duration of IMP exposure

Duration of IMP exposure is defined as last IMP administration date - first IMP administration date +14, regardless of intermittent discontinuations. If the date of the last dose of IMP is missing, the duration of IMP will be left as missing.

Duration of IMP exposure will be summarized quantitatively and categorically: missing duration, <26 weeks, 26 to <52 weeks, 52 to <78 weeks, 78 to <104 weeks, 104 to <130 weeks, 130 to <156 weeks, 156 to <208 weeks, 208 to <260 weeks, 260 to <312 weeks, 312 to <364 weeks, 364 to <416 weeks, 416 to <468 weeks, \geq 468 weeks.

Additionally, the total dose received at each study visit and cumulative duration of treatment exposure over the study period for each patient will be provided in a listing.

Treatment compliance

Compliance to the treatment regimen will be described in terms of the percentage of scheduled infusions the patient receives through the treatment period.

Percentage of treatment compliance for a patient will be defined as $100 \times (\text{Total number of infusions received by a patient from Day 0 to the end of the treatment period or withdrawal}) / (\text{Target total number of expected infusions})$.

Treatment compliance will be summarized quantitatively and categorically: 100%, 85% to <100%, 70% to <85%, 50% to <70%, >0% and <50%.

4.7.2 Adverse events

General common rules for adverse events

All adverse events (AEs) will be coded to a lower-level term (LLT), preferred term (PT), high-level term (HLT), high-level group term (HLGT), and associated primary system organ class (SOC) using the Medical Dictionary for Regulatory Activities (MedDRA) version in effect at Sanofi at the time of database lock.

The AEs will be analyzed in the following 2 categories:

- Pre-treatment AEs: AEs that developed, worsened, or became serious during the pre-treatment period.
- Treatment-emergent adverse events (TEAE)s: AEs that developed, worsened, or became serious during the treatment-emergent period

Deaths during the study period will be provided in a listing.

The primary focus of AE reporting will be on TEAEs. Pre-treatment AEs will be described separately.

An AE with incomplete or missing date/time of onset (occurrence, worsening, or becoming serious) will be classified as a TEAE unless there is definitive information to categorize it as a pre-treatment or a post-treatment AE.

If the assessment of the relationship to IMP is missing for an AE, this AE will be assumed as related to IMP. If the severity is missing for 1 of the treatment-emergent occurrences of an AE, the severity will be imputed with the maximal severity of the other occurrences. If the severity is missing for all the occurrences, the severity will be left as missing.

Multiple occurrences of the same event in the same patient will be counted only once in the tables within a treatment phase.

The AE tables will be sorted as indicated in [Table 4](#).

Table 4 - Sorting of AE tables

AE presentation	Sorting rules
SOC and PT	By the internationally agreed SOC order and decreasing frequency of PTs ^{a, b}

a Sorting will be based on the overall number of patients.

b The table of all TEAEs presented by SOC and PT will define the presentation order for all other tables (eg, treatment-emergent SAE) presented by SOC and PT, unless otherwise specified.

Analysis of all adverse events

The overview of TEAE with event count and number (%) of patients will be generated:

- Any AE
- Any TEAE
 - TEAE related to the study drug
 - TEAE unrelated to the study drug
- TEAEs by severity (mild, moderate, severe)
- TEAEs by gender
- Any treatment emergent SAE
- Any treatment emergent SAE considered related to study drug
- Any protocol-defined infusion-associated reactions
- Any TEAE leading to treatment adjusted
- Any TEAE leading to treatment interrupted
- Any TEAE leading to permanent intervention discontinuation
- TEAE leading to death

The AE summaries of [Table 5](#) will be generated with event count and number (%) of patients experiencing at least one event.

Table 5 - Analyses of adverse events

Type of AE	MedDRA levels
All TEAEs	Primary SOC and PT
TEAEs related to IMP	Primary SOC and PT
TEAEs by maximal severity	Primary SOC and PT
Related TEAEs by maximal severity	Primary SOC and PT
Treatment emergent SAEs	Primary SOC and PT
Treatment emergent SAEs related to IMP	Primary SOC and PT
TEAEs leading to permanent intervention discontinuation	Primary SOC and PT
TEAEs leading to death (death as an outcome of the AE as reported by the Investigator in the AE page)	Primary SOC and PT
Pretreatment AE	Primary SOC and PT

Subgroup analysis

TEAEs stratified by the following categories will also be presented by primary SOC and PT:

- Status of high ADA response (with, without)
- Seroconversion status (negative, positive) and peak ADA categories for those who seroconverted

Analysis of deaths

A listing of patients who died during the study will be provided.

Analysis of infusion-associated reactions (IARs) and other AEs of interest

Protocol-defined IARs

Infusion-associated reactions (IARs) are defined as AEs that occur during the infusion or within up to 24 hours after the start of infusion and are considered as related or possibly related to the ERT by the Investigator or the Sponsor. At the discretion of the Investigator, AEs occurring ≥ 24 hours after the start of the infusion that are assessed as related may also be considered IARs.

Algorithm-defined IARs

An alternative definition of IAR which does not rely on the investigators' assessments of an AE's relationship to the treatment will also be employed. It includes potential IARs (all AEs occurring during an infusion or within 2 hours after the completion of an infusion; and all AEs occurring from >2 to 24 hours after the completion of an infusion).

Protocol-defined infusion-associated reactions and algorithm-defined potential IARs will be selected for analyses as indicated in [Table 6](#). Number of events and number (%) of patients experiencing at least one event will be provided for each event of interest for the IARs. Tables will be sorted as indicated in [Table 4](#).

Anaphylactic/hypersensitivity reactions and immune-mediated reactions

AEs for potential anaphylactic reactions, immune mediated reactions, and hypersensitivity reactions will be identified by respective standardized MedDRA queries (SMQ) (see [Table 6](#)). The results of the searches will be presented in listings. The most recent version of each MedDRA SMQ at the time of analysis will be used.

Table 6 - Selections for IARs and other TEAEs of interest

IARs and other TEAEs of interest	Selection
Protocol-defined IARs	e-CRF specific tick box on the AE page
Algorithm-defined potential IARs	all AEs occurring during an infusion or within 2 hours after the completion of an infusion; and all AEs occurring from >2 to 24 hours after the completion of an infusion
Potential anaphylactic reactions	MedDRA SMQ ^b of anaphylactic reactions
Potential immune mediated reactions	MedDRA SMQs ^b of Vasculitis and Severe cutaneous adverse reactions plus the Preferred Terms of glomerulonephritis, nephrotic syndrome, proteinuria, hematuria, vasculitis, serositis, myocarditis, skin lesion, skin necrosis, arthralgia, arthritis, myalgia, arthropathy, lymphadenopathy, serum sickness, type III immune complex mediated reaction, and influenza like illness ^a
Potential hypersensitivity reactions	MedDRA SMQ ^b of hypersensitivity

^a The list of terms may be adjusted according to MedDRA version changes.

^b The most recent version of each MedDRA SMQ at the time of analysis will be used.

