5.4.5 Missing data

For categorical variables, patients with missing data will not be included in calculations of percentages unless otherwise specified. The analyses and summaries for variables with continuous scales will be based on observed data only.

Handling of Medication Missing/Partial Dates

No imputation of medication start/end dates or times will be performed. If a medication date or time is missing or partially missing and it cannot be determined whether it was taken prior or concomitantly, it will be considered a prior and concomitant medication.

Missing first symptom of Pompe disease

For the calculation of age (months) at first symptom of Pompe disease and time (months) from first symptom of Pompe disease to first alglucosidase alfa infusion, if the month and year are available, the day of the month will be imputed to 15; if, however, only the year is available, the date will not be imputed but left missing.

Missing Assessment of Relationship of Adverse Events to Investigational Medicinal Product

If the assessment of the relationship of the AE to study drug is missing, the event will be considered related to the study drug. However, no imputation will be done at the data level.

Missing Severity of Adverse Events

If the adverse event severity is missing for 1 of the treatment emergent occurrences of an AE, and the maximal severity on the remaining occurrences is mild or moderate, then the worst severity of the event cannot be determined. Therefore, whenever a summary of TEAE by severity is to be presented, these events will be summarized in a separate 'unknown' category.

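### SAP 4.7.2 and 5.4.5 prescribe different severity categories for the same event when one occurrence lacks a grade and the others reach at most mild or moderate

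*SAP*

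**What the plan says.** SAP 4.7.2, in the general rules for adverse events, deals with an event whose severity is missing for one of its treatment-emergent occurrences. In that case "the severity will be imputed with the maximal severity of the other occurrences". The rule has no exception for what that maximum is, and none for whether the other occurrences were related to treatment. The next sentence adds: "If the severity is missing for all the occurrences, the severity will be left as missing".

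SAP 5.4.5, under the heading on missing severity, starts from the same situation. It adds the condition that "the maximal severity on the remaining occurrences is mild or moderate", and concludes: "then the worst severity of the event cannot be determined". Such events go into a separate unknown category "whenever a summary of TEAE by severity is to be presented".

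Three planned outputs tabulate TEAEs by severity. The TEAE overview in 4.7.2 has a line by severity that names three grades and no unknown level. Table 5 has a row for all TEAEs by maximal severity and a row for "Related TEAEs by maximal severity".

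Neither section refers to the other, and neither says which governs.

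**The concern.** The two rules share a trigger and give different answers. If the known maximum is mild or moderate, one rule reports that grade and the other reports unknown, in the same tables. Both cannot be programmed. Left as it is, the choice falls to whoever writes the table programs, possibly with the data in view.

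The choice also has a direction. SAP 4.7.2 counts repeated occurrences of an event in a patient once. In the all-TEAE row by maximal severity, filling the gap with the maximum of the other occurrences therefore gives the same result as ignoring the ungraded one. The same section is cautious elsewhere: an event with missing relationship is taken as related, and one with an incomplete onset date is taken as treatment-emergent unless there is definite information otherwise. Its severity rule, in that row, leans towards the milder reading. What is at stake is how a few events are labelled in the severity tables.

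**Working it through.** The plan gives no figure to reproduce. The check sets the two rules side by side and then bounds the error for a single event.

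**Step 1. Category by case (SAP 4.7.2 and 5.4.5), for TEAEs of any relationship.**

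| Maximum of the other occurrences | 4.7.2 | 5.4.5 | Result |
|---|---|---|---|
| Mild | mild | unknown | conflict |
| Moderate | moderate | unknown | conflict |
| Severe | severe | no rule stated | no conflict; the worst is severe whatever the missing grade |
| No grade known for any occurrence | left missing | no rule stated | no conflict |

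The rules conflict in 2 of the 4 cases.

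**Step 2. Error of the 4.7.2 rule in the all-TEAE row by maximal severity.** Code mild = 1, moderate = 2, severe = 3. Let k be the known maximum and x the true but missing grade. The 4.7.2 rule reports k. The true maximum is max(k, x). The error is k − max(k, x).

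- k = 1: the lowest value is 1 − 3 = −2 and the highest is 1 − 1 = 0.
- k = 2: the lowest value is 2 − 3 = −1 and the highest is 2 − 2 = 0.
- k = 3: 3 − 3 = 0.

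In this row the rule can be too low by up to 2 grades or 1 grade, and cannot be too high.

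**Step 3. Error in the related-TEAE row.** Here only related occurrences belong in the table, but 4.7.2 takes the imputed grade from any other occurrence. Suppose occurrence A is unrelated with a known grade, and occurrence B is related with its grade missing. B is the only related occurrence, so the true value for this row is B's own grade x, and the reported value is A's grade.

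- A severe, B truly mild: 3 − 1 = +2, two grades too high.
- A moderate, B truly mild: 2 − 1 = +1, one grade too high.
- A mild, B truly severe: 1 − 3 = −2, two grades too low.

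The error can go either way. With A severe, 5.4.5 states no rule, so this weakness lies in 4.7.2 alone and remains after the conflict is settled unless the wording is restricted.

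**Step 4. The overview line.** It is not described as maximal severity, so the bound in step 2 is not claimed for it. The conflict applies to it because 5.4.5 covers every TEAE summary by severity, and the line as written has no place for an unknown level.

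**Step 5. Outputs affected.** 1 overview line + 2 Table 5 rows = 3.

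These are bounds for one event. They are not frequencies.

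**The case against.** The best defence is that 5.4.5 is the narrower rule: it is limited to a mild or moderate known maximum and to severity summaries, so a programmer could treat it as an exception to the general rule in 4.7.2. That is a sensible reading, and it points to the preferred fix. But the SAP does not say it, and the sections cannot be combined as imputation in the data with unknown in the tables. Imputing the maximum of the others settles the worst grade, which 5.4.5 says cannot be settled, and the severity summaries are where an imputed grade would be used. The sentence in 5.4.5 that rules out imputation at data level stands under the relationship heading and does not cover severity.

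A second defence is that missing grades should be rare. Investigators are asked to grade severity (protocol 9.5.1), missing data are to be explained (protocol 10.1) and sites are contacted for corrections (protocol 10.2). This stands, and it lowers the priority.

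Three stronger readings are tempting and are not supported:

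- A reader might infer that the 4.7.2 rule always understates severity, or is exact whenever the known maximum is severe. Step 3 shows that neither holds for related TEAEs.
- A reader might infer that the two sections conflict for all missing severities. They do not when the known maximum is severe or when no grade is known.
- A reader might infer that the percentage denominators are also in conflict, because 5.4.5 says that "patients with missing data will not be included in calculations of percentages unless otherwise specified". Giving these events a category of their own can fairly be read as specifying otherwise. A sentence on the denominator would be an optional clarification, separate from this point. The same holds for events with more than one ungraded occurrence, where both sections share the same limited wording.

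**Conclusion.** The contradiction is real and confined to one situation: one treatment-emergent occurrence without a grade, with the others reaching at most mild or moderate. SAP 4.7.2 then gives mild or moderate, and 5.4.5 gives unknown. Three outputs depend on the choice. For a single affected event, the 4.7.2 value in the all-TEAE row is at most 2 grades too low (known maximum mild) or 1 grade too low (moderate), and never too high. In the related-TEAE row it can be too low or too high. The latter result rests on reading 4.7.2 literally, with no restriction of the other occurrences to related ones.

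Priority is low. SAP 4.7 makes the safety analyses descriptive with no testing planned, protocol section 11 also lists all adverse events by patient, and SAP Appendix 2 (section 5.2) reports 12 patients enrolled. The documents do not say how many grades are missing. The number may be zero, so no effect on the tables can be stated, and a reader should not infer that the severity tables are distorted.

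**What to change.** Before the tables are produced, put one rule in both sections. The rule of 5.4.5 is preferable, because it does not assign a grade that the data leave open. SAP 4.7.2 could be amended along these lines:

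- Severity missing for one occurrence, and the known maximum over the occurrences eligible for that table is mild or moderate: the event is summarized as unknown, per 5.4.5.
- That known maximum is severe: the maximal severity is severe.
- All eligible severities are missing: the severity is left as missing.

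SAP 5.4.5 should carry the same reference to eligible occurrences. This restriction matters for the related-TEAE row; without it, an unrelated occurrence could still set the grade there.

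Add an unknown level to the overview line by severity and to the two Table 5 outputs by maximal severity.

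The cost is a few reworded sentences and one extra level in three table shells. No new data are needed. The downside is one more category to display and slightly fewer events with an assigned grade.

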
NAME OF COMPANY Genzyme Corporation, a Sanofi Company [name]	SUMMARY TABLE Referring to Part ..... of the Dossier: Volume: Page: Reference:	FOR NATIONAL AUTHORITY USE ONLY:
NAME OF FINISHED PRODUCT Myozyme® / Lumizyme® (alglucosidase alfa)		
NAME OF ACTIVE INGREDIENT alglucosidase alfa		
variables, frequencies and percentages will be presented. For continuous variables, descriptive statistics (n, mean, median, standard deviation, minimum, and maximum) will be presented.		
Analyses will be performed using the SAS® statistical software system. Detailed descriptions of the analyses will be provided in a Statistical Analysis Plan.		
Baseline demographic and background variables will be summarized for the patients enrolled in the study using descriptive statistics.		
In addition to descriptive statistics by visit, longitudinal repeated measures modeling will be used to analyze the trends in key growth and development parameters over time.		
Analyses of key variables may be stratified by relevant baseline factors.		
Besides standard safety analyses of the incidence of AEs and SAEs, additional analyses will be carried out to examine the trends in incidence and prevalence of AEs, SAEs and other relevant safety parameters over time. Key safety analyses will be also carried out by gender.		
EXPLORATORY: The effect of alglucosidase alfa treatment on urinary oligosaccharides (Hex4) will be evaluated.		
RESEARCH PURPOSES ONLY: The potential effect of CRIM status and GAA mutation on efficacy outcomes will be analyzed.		

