## **11. STATISTICAL METHODS AND PLANNED ANALYSES**

Prior to data analysis, all data editing will be complete and decisions regarding the evaluability of all patient data for inclusion in the statistical analysis will be made. The rationale for excluding any data from the statistical analyses will be prospectively defined prior to commencing with statistical analysis, as part of the Statistical Analysis Plan.

The Genzyme Department of Biostatistics will perform the statistical analysis of the data derived from this study. Details of the statistical analysis will be specified in the Statistical Analysis Plan. Analyses will be performed using the SAS® statistical software system.

All enrolled patients who receive at least one infusion (complete or partial) of alglucosidase alfa in this study will comprise the analysis population for the efficacy and safety analyses.

All data collected will be presented in the form of individual patient listings. Provided the data are not too sparse, summary tables will be created for the efficacy and safety variables.

Continuous variables will be summarized using descriptive statistics (n, mean, median, standard deviation, minimum and maximum). Categorical variables will be summarized using frequencies and percentages.

Baseline demographic and background variables will be summarized and also presented in patient listings. Efficacy endpoints include physical growth, development, and cognitive function.

Physical growth is assessed by body height/length, weight and head circumference. Changes from baseline to study time points will be summarized descriptively for body height/length, weight and head circumference. Changes in Z-scores (standardized age and gender adjusted values) for height/length, weight and head circumference with reference to Center for Disease Control (CDC) Growth Charts will also be summarized descriptively.

The Bayley-III consists of 3 administered scales – cognitive, language and motor and will be administered to patients from 1 month to 42 months of age. Changes from baseline to study time points in the raw scores, scaled scores and composite scores reported for each of the 3 administered scales will be summarized descriptively.

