3 ANALYSIS POPULATIONS

The following population for analyses is defined:

Table 3 - Populations for analyses

Population	Description
Full Analysis Set (FAS)	All enrolled patients who receive at least one infusion (complete or partial) of alglucosidase alfa. This study population will be used for all analyses (efficacy and safety), unless otherwise specified.

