4 STATISTICAL ANALYSES

4.1 GENERAL CONSIDERATIONS

In general, continuous data will be summarized using the number of observations available, mean, standard deviation (SD), median, minimum, and maximum. Categorical and ordinal data will be summarized using the counts and percentages of patients.

The baseline value is defined as the value measured at the Screening/Baseline visit prior to the first infusion during this study. In cases where a patient has more than one value measured during Screening/Baseline, the latest value will be the one used as baseline.

Unless otherwise specified, analyses will be performed for Full Analysis Set (FAS).

Observation period

The observation period will be divided into 2 segments:

- The **pre-treatment period** is defined as the period up to first IMP administration (ie, when the patients started receiving the alglucosidase alfa in the study, even if the patient had received alglucosidase alfa prior to entering the study).
- The **on-treatment period** (ie, treatment-emergent (TE) period) is defined as the period from the first IMP administration in the study to the last study assessment.

The on-study period is defined as the time from the signing of the informed consent until the end of the study (defined as the completion date or the discontinuation date collected on the case report form (CRF) page “Completion/Discontinuation”).

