4.2 PATIENT DISPOSITIONS

The number (%) of patients included in the analysis population listed in [Table 3](#) will be summarized.

The number (%) of patients in the following categories will be provided:

- Screened patients
- Enrolled patients
- Enrolled and treated patients
- Patients who completed the study period as per protocol
- Patients who did not complete the study period as per protocol and main reason for study discontinuation
- Patient status at last study contact (alive, deceased)

A listing will be provided with completion/discontinuation dates, study duration (days), and all discontinuation reasons.

Protocol deviations

Critical and major protocol deviations (automatic or manual) will be summarized in the enrolled population.

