5.2 APPENDIX 2 CHANGES TO PROTOCOL-PLANNED ANALYSES

Regarding the calculation of z-scores for physical growth (recumbent length/height, weight, head circumference) the protocol referred to Center for Disease Control (CDC) Growth Charts. However, the CDC website recommended the World Health Organization (WHO) growth charts for children <24 months of age. If possible, we will incorporate this recommendation. In addition, percentiles of these measurements will be calculated as well.

It was planned to use longitudinal repeated measures modeling to analyze trends in key growth and development parameters over time; however, as out of the 12 patients enrolled 7 patients had withdrawn or died in less than 4 years, this analysis is not likely to be informative and will be omitted.

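### The AE and SAE time trends promised in the protocol synopsis are absent from SAP 4.7.2, and the SAP does not declare the omission

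*SAP*

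**What the plan says.** **Protocol.** The statistical part of the synopsis says that, besides the usual AE and SAE incidence, "additional analyses will be carried out to examine the trends in incidence and prevalence of AEs, SAEs and other relevant safety parameters over time". Section 11 describes only frequencies and percentages of patients and of events for AEs, SAEs and IARs. It neither repeats the commitment nor withdraws it. It also carries a general condition: "Provided the data are not too sparse, summary tables will be created for the efficacy and safety variables".

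**SAP, AE tables.** Section 4.7.2 has an overview and Table 5, whose summaries "will be generated with event count and number (%) of patients experiencing at least one event". The on-treatment period in section 4.1 "is defined as the period from the first IMP administration in the study to the last study assessment". It starts at the first study infusion, "even if the patient had received alglucosidase alfa prior to entering the study". The analysis set in section 3 is "All enrolled patients who receive at least one infusion (complete or partial) of alglucosidase alfa".

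**SAP, time-related output.** Section 4.7.1 summarises exposure duration in 13 intervals plus a missing category, and the share of patients treated up to given times. Section 4.7.3.1 summarises laboratory values and ECG measurements at each planned visit. On disposition, section 4.2 states: "A listing will be provided with completion/discontinuation dates, study duration (days), and all discontinuation reasons".

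**SAP, declared changes.** Appendix 2 covers the growth charts and percentiles, and the omission of repeated-measures modelling because "out of the 12 patients enrolled 7 patients had withdrawn or died in less than 4 years". Table 1 removes summary tables for efficacy endpoints only. Neither mentions AE trends.

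**The concern.** Long-term safety is the study's secondary objective, and the planned follow-up is ten years. A count and a percentage pooled over each patient's whole time on study cannot show whether AEs rise, fall or cluster early. Follow-up here is also very unequal, so one printed percentage can describe different situations: 5 of 12 patients affected in the first year, or all 5 of the patients still observed years later.

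The silence is a second problem. Appendix 2 exists to record departures from protocol-planned analyses, and it explains one dropped time analysis (growth and development) but not the other (AEs). A reader cannot tell a decision from an oversight.

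**Working it through.** The plan states no figure on this point to reproduce. The check is a comparison of texts followed by simple bounds.

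**1. Promise against delivery**
- AE and SAE incidence over time: promised in the synopsis. SAP 4.7.2 splits AEs by severity, relatedness, gender and ADA status, but not by study time.
- AE and SAE prevalence over time: promised. No table counts ongoing events.
- Other safety parameters over time: served by the by-visit laboratory and ECG summaries.
- IAR windows in SAP 4.7.2 (up to 2 hours, and more than 2 to 24 hours) run from an infusion, not from study entry, so they show no long-term trend.
- Declared as changed: no, in either Table 1 or Appendix 2.

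**2. Patients observed late.** Inputs from Appendix 2: 12 enrolled, 7 gone before four years.
- Observed after year 4: at most 12 − 7 = 5.

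**3. Ceiling for a late AE.** Percentages use the Full Analysis Set. The documents do not give its size, so I assume all 12 were infused and show smaller sets as a range. For an AE type with no occurrence before the end of year 4:
- 12 infused: 5/12 = 41.7%
- 11 infused: 5/11 = 45.5%
- 10 infused: 5/10 = 50.0%

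Each ceiling applies even if 5 of 5 patients at risk had the event. Five of 12 affected in year 1 also gives 41.7%.

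**4. Observation time, conditional on when follow-up stops**
- Assuming a stop at 10 years: total below 7 × 4 + 5 × 10 = 78 patient-years, against 12 × 10 = 120 planned (65%). After year 4, at most 5 × 6 = 30.
- The SAP analysis windows run to day 3836 for IgG and day 4018 for Hex4, and 4018/365.25 = 11.0 years. With 11 years as the limit, the total is below 28 + 55 = 83, and at most 5 × 7 = 35 falls after year 4.

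**5. Time origin.** The oldest patient was 1.9 years at consent (SAP 5.4.3), and treatment had to begin before age 1 (protocol 7.1). That patient therefore started treatment at least about 1.9 − 1.0 = 0.9 years before consent. Study time is not time since first treatment for everyone.

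**6. Precision of a by-period table.** With at most 5 at risk after year 4, one patient moves a yearly percentage by at least 1/5 = 20 points.

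**The case against.** The best case for the plan has four parts.

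*The SAP matches section 11.* This is true: frequencies and percentages are what section 11 asks for, and the promise stands only in the synopsis. The opening of the synopsis statistics text is missing from the extract available for this review, so a qualifier there cannot be excluded. But section 11 does not withdraw the commitment. If it was meant to override the synopsis, Appendix 2 is the place to say so.

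*Timing can be recovered from other output.* Much of this stands. The exposure tables in SAP 4.7.1 come close to showing numbers at risk, mean duration times the number of patients gives total exposure, and section 11 promises individual AE listings. Still, exposure there ends 14 days after the last infusion, whereas AEs are counted to the last study assessment. Nothing planned joins AEs to time, and a reader would have to assemble it by hand.

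*The data are too sparse.* This may be a good reason, and the argument used for dropping the modelling would apply here too. The SAP does not invoke it for AEs, and it plans SOC and PT tables within ADA strata in the same small cohort.

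*A by-year table could mislead.* This stands as a caution. The cohort falls from at most 12 to at most 5 through withdrawal and death, so an apparent trend may reflect who remained.

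A reader might also infer that late toxicity will be hidden, or that the omission was deliberate. The documents support neither: every AE is to be listed by patient, and no reason for the omission is given either way.

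**Conclusion.** The point holds as an undeclared gap between the protocol synopsis and the SAP, and it should be corrected. At most 5 of 12 enrolled patients can inform AE experience after year 4. The planned tables cap an AE type first arising then at 42% if all 12 were infused (45% or 50% with 11 or 10), and they cannot distinguish that from the same count in year 1.

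Five of 12 rests on Appendix 2 alone. The patient-year totals (under 78 overall, at most 30 after year 4) need the further assumption that follow-up stops at ten years and should not be quoted without it. No bias in a particular result is shown. The synopsis does not promise exposure-adjusted rates, so their absence is not in itself a departure. The ADA-stratified tables and the rule for counting repeated events are separate matters on which nothing here depends.

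**What to change.** Either restore the analysis in simple form or declare its omission.

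**Restore.** Add one descriptive table for TEAEs, SAEs and IARs by study period, for example by year with later years grouped. For each period show patients at risk, patients with a new event, number of events and observation time. Add a row for unknown onset, because SAP 4.7.2 classes AEs with missing onset as treatment-emergent unless there is definite information otherwise. Add patients with an ongoing event, which is the prevalence half of the promise, if AE stop dates are available. Protocol 9.5.3 shows only that the outcome of ongoing events is recorded, so stop dates are an assumption.

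Footnote three things: time starts at the first study infusion; some patients were treated before it; and the cohort shrinks through withdrawal and death, so differences between periods may reflect who remained.

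**Or declare.** State in Appendix 2 that the trend analysis is omitted and why, citing the sparseness condition if that is the reason.

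**Cost.** One table with footnotes, or one Appendix 2 entry. Apart from the ongoing-event row, no new data should be needed. Late-period figures will be coarse (at least 20 points per patient), so label the table descriptive and draw no inference from it.
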